Study Objectives	1. Primary objective is to estimate the clinical response as quantified by irRECIST 1.1 to hypofractionated radiotherapy with nelfinavir and anti-PD1/PDL1 immunotherapy. 2. Secondary objectives are to evaluate late toxicity, immune-related clinical responses and immune pharmacodynamic changes hypofractionated radiotherapy with nelfinavir and anti PD1/PDL1 immunotherapy
Diagnosis and Main Inclusion Criteria	Patients with previously untreated or previously treated metastatic melanoma, NSCLC, or renal cell carcinoma with bone, lung, liver, or subcutaneous or nodal involvement but without evidence of brain involvement. Patients who have previously been treated with radiation will be included in the study, so long as a suitable plan for treatment can be developed. Patients who have received prior immunotherapy will be included in the study and enrolled into a separate stratum.
Study product, dose, route, regimen	Hypofractionated Image Guided Radiation Therapy. Three fractions of 800cGy each given over 3-14 days. Pembrolizumab, Nivolumab, or Atezolizumab per standard dosing and schedule. Nelfinavir: 1250 mg PO BID administered for 7 – 14 days prior to start of immunotherapy, for a total of 11-12 weeks.
Duration of administration	Radiation treatment to be delivered over 3-14 days with concurrent Nelfinavir and Immunotherapy. Subjects will take nelfinavir for a total of 11-12 weeks. Immunotherapy will continue per the FDA-approved dosing schedule.
Reference Therapy	FDA-approved PD-1 or PD-L1 inhibitors
Number of trial subjects	The expected accrual rate = 30 pts/yr. The protocol is designed for a maximum total of 120 patients (10 patients per year for melanoma and 10 patients per year for NSCLC and 10 patients per year for RCC).
Study Duration	The expected total study duration is 4 to 4 1/2 years needed to complete accrual.
Statistical Methodology	This is a stratified phase II study of hypofractionated radiotherapy combined with immunotherapy for previously untreated or previously treated metastatic melanoma, NSCLC, and renal cell carcinoma patients. Phase II is stratified by histology and whether or not the patient has received prior immunotherapy. We will also collect serum for correlative studies.

Table of Contents

1.0	INTRODUCTION TO THE PROTOCOL	6
1.1	Introduction.....	6
1.2	Preclinical Data.....	7
1.3	Clinical Data to Date.....	10
1.4	Reference Therapy: PD-1 and PD-L1 Inhibitors.....	12
1.5	Dose Rationale	15
1.6	Other Agents.....	15

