Based upon our pre-clinical data, we performed a phase I/II trial of nelfinavir with concurrent chemoradiotherapy in patients with inoperable locally advanced NSCLC. The objective of the phase I trial was to determine dose-limiting toxicities (DLT) and the maximally tolerated dose of nelfinavir in combination with concurrent chemoradiotherapy (CT-RT) in locally advanced non-small cell lung cancer (NSCLC). We administered nelfinavir according to the following schema dose Level (DL) 1: 625mg PO BID, DL2:1250mg PO BID was given for 7 to 14 days prior to and concurrently with concurrent CT-RT to patients (pts) with biopsy confirmed IIIA or IIIB unresectable NSCLC. Five patients were treated at DL1; 7 patients were treated at DL2. Patients were treated with concurrent CT-RT to a dose of 66.6Gy. DLTs were defined as any treatment related Grade 4 hematologic toxicity requiring a break in therapy or non-hematologic Grade 3 or higher toxicity except esophagitis and pneumonitis. Sixteen patients were enrolled and 12 patients were treated with nelfinavir and concurrent chemoradiotherapy. No DLTs have been observed at either dose level. The maximum tolerated dose of

[figure not shown]

Figure 5 Mechanism of synergy between high-dose radiotherapy, nelfinavir, and checkpoint inhibition to achieve durable anti-tumor immune memory (Adapted from Hodge et al Oncology 2008)

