6.11 Patient Replacement

A patient who is enrolled but did not receive any protocol therapy (one dose of PD1/PDL1 immune checkpoint inhibitor) is considered non-evaluable, and will be replaced.

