11.0 STATISTICAL CONSIDERATIONS

11.1 Sample Size with Power Justification

The primary objective of this study is to evaluate the response rate in patients with non-small cell lung cancer (NSCLC), melanoma, or renal cell carcinoma (RCC) treated with nelfinavir, radiation therapy and anti-PD-1/PD-L1 therapy. Evaluation of this investigational therapy will be done in disease-specific cohorts separately evaluated by patients naïve to anti-PD-L1/PD-L1 therapy and those with disease refractory to anti-PD-1/PD-L1 therapy.

The total sample size for this study is 20 patients in each of the 6 cohorts (3 disease type by 2 anti-PD-1/PD-L1 exposure groups) for a total of 120 patients evaluable for response. The expected accrual rate is 30 patients per year. The design within each cohort is a single arm, single stage design. The sample size justification for each of the cohorts is follows. Sample size calculations were done using this calculator: <https://stattools.crab.org/Calculators/oneArmBinomial.html>.

Non-Small Cell Lung Cancer (NSCLC):

1. Checkpoint Naïve: In this cohort a true response rate of 50% or greater would be considered evidence of activity whereas a response rate of 25% or less (based on historical data) would not be considered of interest. With 20 patients, this study has 86% power to rule out a response rate of 25%, at the 1-sided 0.10 level if the true response rate were 50%. The observation of at least 8 responses (8/20; 40% ORR) would be

considered evidence to rule out a response rate of 25%. The exact power and type I error for this design are 87% and 10%, respectively.

2. Checkpoint refractory: In this cohort a true response rate of 25% or greater would be considered evidence of activity whereas a response rate of 5% or less (based on historical data) would not be considered of interest. With 20 patients, this study has 91% power to rule out a response rate of 5%, at the 1-sided 0.10 level if the true response rate were 25%. The observation of at least 3 responses (3/20; 15% ORR) would be considered evidence to rule out a response rate of 5%. The exact power and type I error for this design are 91% and 7.6%, respectively.

Melanoma:

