11.2 Analysis Plan

The primary analysis within each cohort will done on patients who receive at least one dose of nelfinavir, and anti-PD-1/PD-L1 therapy and at least one fraction of radiation. The safety analysis population will include all patients who receive at least one dose of any of the study drugs.

Binary endpoints (response, toxicity) will be summarized as proportions with associated 90% Clopper-Pearson confidence intervals. With 20 patients per cohort, binary proportions can be estimated to within 18% with 90% confidence. Any toxicity with true prevalence of at least 10% is likely to be observed (with 88% probability).

The distribution of time-to-event endpoints will be estimated using the method of Kaplan-Meier to derive estimates for median times and percentages at landmark times (e.g. 6 months). Confidence intervals for median times will be estimated using the Brookmeyer-Crowley method and for landmark times will be calculated using Greenwood's formula and based on a log-log transformation applied on the survival function.

A logistic regression model will be used to assess the association between response and factors such as smoking within each cohort. These associations will be summarized by odds ratios and associated confidence intervals and p-values. A Cox regression model will be used to assess the association between time-to-event outcomes (PFS,OS) and factors within each cohort. Similarly, these associations will be summarized by hazard ratios and associated confidence intervals and p-values.

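### Enrolment is capped at 120 while the power assumes 120 evaluable patients, and the replacement rule omits patients who receive no radiation, so any non-evaluable patient costs power

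*Combined protocol and SAP*

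**What the plan says.** The synopsis, under the number of trial subjects, says "The protocol is designed for a maximum total of 120 patients". Section 11.1 says "The total sample size for this study is 20 patients in each of the 6 cohorts", "for a total of 120 patients evaluable for response". It adds that "The design within each cohort is a single arm, single stage design" and gives each cohort one response count, for n=20 only: 8 for naive NSCLC and naive RCC, 3 for refractory NSCLC and refractory RCC, 11 for naive melanoma and 5 for refractory melanoma.

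Section 6.11 covers enrolled patients who received no protocol therapy, which it defines in parentheses by the checkpoint inhibitor alone: "one dose of PD1/PDL1 immune checkpoint inhibitor) is considered non-evaluable, and will be replaced". The primary analysis population in 11.2 is narrower. It requires a dose of nelfinavir, a dose of checkpoint inhibitor and "at least one fraction of radiation".

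Two other places end at 120: the pooled hepatotoxicity boundaries in 11.3, whose last band is 118 to 120 patients, and the planned enrolment table in 11.4. No section gives an expected non-evaluable proportion or an enrolment inflation.

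**The concern.** An enrolment maximum of 120, a requirement for 120 evaluable patients and a rule that replaces some patients cannot all be met once one enrolled patient is non-evaluable.

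The second gap remains even if the cap is lifted. Under 6.2, radiation starts after the first checkpoint inhibitor dose and before the third cycle. A patient who progresses, has toxicity or withdraws in that interval has had immunotherapy, so 6.11 does not replace them. They have had no radiation, so 11.2 excludes them. The rule in 2.3.1 that codes unknown responses as non-responses does not restore them, because they have already left the analysis population.

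What is at stake is the power that 11.1 presents as delivered. There is also no stated decision rule for a cohort that ends with fewer than 20, so a threshold would have to be chosen late, possibly with the responses known.

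**Working it through.** **Inputs.** From 11.1, as null rate, target rate and count at n=20: naive NSCLC/RCC 25%, 50%, 8; refractory NSCLC/RCC 5%, 25%, 3; naive melanoma 43%, 68%, 11; refractory melanoma 15%, 40%, 5. The loss rate is not in the documents; 5% to 20% is assumed here to show a range.

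**Formula.** For X ~ Binomial(n, p) and count r, type I error is P(X ≥ r) at the null rate and power is P(X ≥ r) at the target rate.

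**Step 1: reproduce the plan at n=20.** Exact power and type I error are 86.8% and 10.2% (stated 87% and 10%), 90.9% and 7.5% (stated 91% and 7.6%), 92.8% and 19.5% (stated 93% and 19.5%), and 94.9% and 17.0% (stated 95% and 17%). The plan's exact figures are confirmed. Its nominal powers are 86%, 91%, 84% and 90% for the same four designs.

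**Step 2: keep the stated count and reduce n.** Power:

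| Cohort (count) | n=20 | 19 | 18 | 17 | 16 |
|---|---|---|---|---|---|
| Naive NSCLC/RCC (8) | 86.8% | 82.0% | 76.0% | 68.5% | 59.8% |
| Refractory NSCLC/RCC (3) | 90.9% | 88.9% | 86.5% | 83.6% | 80.3% |
| Naive melanoma (11) | 92.8% | 88.1% | 81.2% | 71.6% | 59.3% |
| Refractory melanoma (5) | 94.9% | 93.0% | 90.6% | 87.4% | 83.3% |

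One entry by hand: with n=17 and p=0.5, P(X ≥ 8) = 0.5 + C(17,8)/2^17 = 0.5 + 24310/131072 = 0.6855.

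One lost patient takes naive NSCLC/RCC below its nominal 86% and refractory NSCLC/RCC below 91%. Naive melanoma passes below 84% at n=18. Refractory melanoma stays above 90% down to n=18.

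**Step 3: type I error.** At n=19 with the same counts it is 7.8%, 6.7%, 14.0% and 14.4%. It falls in every cohort.

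**Step 4: is the count or the sample size responsible?** For naive NSCLC/RCC, 8 is the smallest count with type I error at or below 0.10 at n=17, 18 and 19. For refractory NSCLC/RCC, 3 is the smallest at every n from 15 to 20. In those ranges the loss comes from having fewer patients, and changing the count would not recover it within the 0.10 level. The count matters for naive NSCLC/RCC at n=16, where 7 gives type I error 8.0% and power 77.3% against 59.8% with 8, and at n=15, where 7 gives 5.7% and 69.6% against 50.0% with 8.

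**Step 5: how likely is a full cohort under the cap?** If each patient is independently non-evaluable with probability d, the chance that all 20 are evaluable is (1−d)^20. This is 0.95^20 = 36% and 0.90^20 = 12%.

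**Step 6: enrolment for 20 evaluable per cohort.** 20/(1−d), rounded up, is 22, 23, 24 or 25 at 5%, 10%, 15% or 20%. Over six cohorts that is 132, 138, 144 or 150.

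**The case against.** The strongest reply is that the synopsis figure may be meant as a count after replacement. Section 11.1 speaks of evaluable patients, 6.11 provides for replacement, and the synopsis duration of 4 to 4.5 years at 30 per year gives 120 to 135 patients, so the timeline has some room (120/135 = 89%, or about 11% loss). That reading is possible. However, the 11.3 boundaries, which pool all patients on trial, and the 11.4 enrolment table both stop at 120, so the documents do not settle it. Nor does that reading close the gap between 6.11 and 11.2.

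A reader might infer three stronger things, and none is supported.

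- That the cohorts will fall short. This depends on a loss rate the documents do not give.
- That the sponsor's own phase I trial sets that rate at 25%, since "Sixteen patients were enrolled and 12 patients were treated with nelfinavir and concurrent chemoradiotherapy". That trial gave chemoradiotherapy without a checkpoint inhibitor, and the text does not say why four patients went untreated. Patients who never reach a checkpoint inhibitor dose are the ones 6.11 does replace. The figure does not measure the loss between immunotherapy and radiation.
- That the fixed counts themselves fail at smaller n. They become stricter, and in NSCLC and RCC at n=17 to 19 they are still the smallest counts that hold the 0.10 level.

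It is also fair to say that the 90% Clopper-Pearson intervals in 11.2 are valid at any n, so estimation is not damaged beyond some loss of precision.

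**Conclusion.** The point holds in conditional form. If any enrolled patient is non-evaluable, the current text cannot deliver both the cap and the evaluable number. Patients without radiation are lost with no replacement whichever way the cap is read.

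The cost of the first lost patient in a cohort is about 5 points of power in each naive cohort and about 2 points in each refractory cohort. By n=16 power is about 60% in the naive cohorts and 80% to 83% in the refractory ones. These figures rest on the null and target rates in 11.1 and on keeping the stated counts. The 36% and 12% chances of a full cohort rest on the assumed loss rates and on independence between patients. False-positive risk does not rise. This is worth correcting because the stated power is conditional on zero loss and the plan does not say so.

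**What to change.** 1. Align the 6.11 replacement rule with the 11.2 analysis population, so that every patient excluded from the primary analysis is either replaced or explicitly counted as an unreplaced loss.
2. Make the synopsis and 11.1 agree. Either state 120 as evaluable, with replaced patients not counted, give the higher enrolment maximum, and extend the 11.3 boundaries and the 11.4 table past 120; or keep 120 as the enrolment maximum and restate power for the expected evaluable number under a labelled loss assumption.
3. Add to 11.1 the decision count, with exact type I error and power, for each cohort at n below 20. To hold the 0.10 level, naive NSCLC/RCC needs 8 at n=17 to 19 and 7 at n=15 to 16. Refractory NSCLC/RCC needs 3 throughout n=15 to 20. In melanoma the stated counts have exact type I errors of 19.5% and 17% at n=20, so the sponsor should first say which level applies. At 0.10, naive melanoma needs 12 at n=19, 11 at n=17 to 18 and 10 at n=16; refractory melanoma needs 6 at n=18 to 19 and 5 at n=16 to 17.

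Cost: a few sentences and a small table. Restating power makes the stated figures somewhat less favourable and adds no patients. The evaluable option adds about 12 to 30 patients at an assumed 5% to 20% loss (132 − 120 to 150 − 120).

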CMV ^d	X								
Pregnancy Test ^e	X								
Research Blood Collection ^{g, h}	X	X	X	X	X	X	X		
Treatment									
Nelfinavir ^g			X	X	X	X	X		
Immunotherapy ^j				X	X	X	X	X	X ^j
3 days x 6-8 Gy ^f				X	X	X	X		

KEY

- a. Baseline within 2 months of study entry. Repeat every 10-12 weeks or as clinically indicated
- b. Within 2 months of study entry
- c. Optional biopsy at end of service
- d. Within 30 days of study entry
- e. For WOCP^j; Within 7 days of study entry
- f. A CT simulation will be scheduled to plan for 3 fractions of 6-8gy each to a single lesion. Radiation will commence between 1st and 3rd dose of immunotherapy.
- g. Research Procedure
- h. 8 yellow top BD #364606 + 1 red top # BD 367820 ([name] specimen processing)
- i. Pembrolizumab, Nivolumab, or Atezolizumab. Continue until progression.

1.0 INTRODUCTION TO THE PROTOCOL

This document is a protocol for a human research study. This study is to be conducted according to US and international standards of Good Clinical Practice (FDA Title 21 part 312 and International Conference on Harmonization guideline), applicable government regulations and Institutional research policies and procedures.

1.1 Introduction

Therapies targeting immune check points represent one of the most exciting breakthroughs against lung cancer, notwithstanding the targeted therapies against known driver mutations. These therapies that target immune check points have the capability to dramatically change the field and provide a more physiological way of harnessing innate immune responses against the patient's tumors. Several studies have been published/ongoing studying various aspects of PD1/PD-L1 or CTLA4 and they are summarized in recent reviews (1)

Non-small cell lung cancers (NSCLCs) are among the solid tumors with the highest frequency of somatic mutations (8.17 and 6.43 mutations per Mb (Megabase) for the squamous and non-squamous subtype, respectively), only surpassed by melanoma at 13.2 mutations per Mb (2). These mutations, likely secondary to DNA damage from cigarette smoke and UV exposure, have the potential to generate tumor-rejection antigens. However, the vast majority of lung cancers successfully evade elimination by the immune system. This is in part attributable to the expression by cells in the tumor microenvironment of molecules such as PD-L1 that engage cognate inhibitory receptors (PD-1) expressed on T cells. PD-L1 is expressed by cells in many lung cancers, either constitutively or in response to cytokines produced by tumor-infiltrating T cells. Signaling through the PD-1/PD-L1 axis can inhibit cytokine production and cytolytic activity of CD8+ and CD4+ T cells that have migrated into the tumor. The last decade has witnessed the development of several novel agents that block these immune "checkpoints" (3) Inhibiting PD-L1 and dis-engaging PD-1 on T cells in cancer patients can reverse the adaptive immune resistance, and enhance T cell-mediated anti-tumor immunity (4)

Early studies with anti-PD-L1 antibodies in patients with a variety of tumor types have shown response rates of 25-34%, with some durable responses (5). Interestingly, tumors with the greatest mutational load and heterogeneity, such as NSCLC, melanoma, and renal cell carcinoma, demonstrated the greatest benefit. Recent data suggest that both tumor heterogeneity and PD-L1 expression are associated with higher response rates to PD-L1-directed therapies (5). Aside from tumor PD-L1 expression, success of the anti-PD-L1 therapy relates to the presence of pre-existing immunity that is suppressed by PD-1/PD-L1 signaling and becomes re-invigorated following therapy with PD-L1 blockade(6). Herbst et al. demonstrated a systemic re-priming and expansion of both pre-existing antitumor T-cell and non-tumor-directed T-cell populations in the peripheral blood (5). Other studies in melanoma and prostate cancer patients have revealed that specific host T cell repertoire, determined by next-generation sequencing (of T cell receptor, TCR sequence usage) have revealed that a less diverse, more clonal population accurately predicted responders from non-responders to immune check-point blockade (7).

Preclinical data demonstrates that radiation can improve responses of lung cancer to PD-L1 immunotherapy (4). The mechanisms of cooperation and improved disease control have not been clearly established but may include: (1) enhanced immunogenic antigen presentation (2) stimulation of cytokine release; and (3) enhanced PD-L1 expression on the tumors resulting from change in the stromal lymphocyte infiltration induced by XRT. Blockade of PD-L1 near the time of radiotherapy may enhance the native lymphocyte response. The role of hypofractionated or SBRT/HIGRT-induced tumor antigen release in the era of combination checkpoint inhibition: Higher doses of XRT delivered over shorter fractions have the ability to increase antigen presenting cells (8). Wolchok et al. recently reported a 40% response rate to combination therapy, with all patients achieving greater than 80% or more reduction in tumor burden in advanced melanoma. In our proposed model, HIGRT/SBRT is complementary to immune checkpoint inhibition and would be anticipated to augment combination therapy.

1.2 Preclinical Data

Nelfinavir and radiosensitization:

We and others have been attempting to identify a common downstream signal that is associated with radiation resistance. Data from our laboratory have demonstrated that inhibition of Ras and/or the downstream PI3K-Akt pathway increases the radiosensitivity of cells in which this pathway is activated but does not affect cells without activation of this pathway (including normal tissues)(9, 10). We have both preclinical and clinical experience with farnesyltransferase inhibitors as radiation sensitizers (11, 12). However, inhibition of targets downstream of Ras including PI3K may provide a more effective target as this pathway is affected by both mutations and/or overexpression of EGFR, PTEN, Ras, and others. There are, however, currently no clinically useful inhibitors of PI3K. PI3K phosphorylates PtdIns-4, 5-P2 to yield PtdIns-3, 4, 5-P3. PtdIns-3, 4, 5-P3 in turn causes membrane localization of protein kinase B (PKB/Akt) and the phosphoinositide-dependent kinases (PDK's) which phosphorylate Akt (13). Akt thus is an immediate downstream target of PI3K.

It has been reported that the activation (phosphorylation) of Akt by insulin is reduced in the presence of the HIV protease inhibitor (HPI) NFV (nelfinavir) (14). HPIs have also been reported to cause insulin resistance and diabetes(15). We know that Akt signaling plays a role in insulin signaling so we speculated that these side-effects of HPIs might be due to interference with Akt signaling. Our hypothesis is that HPI's will inhibit Akt signaling and radiosensitize human tumors as a result. Akt is a serine/threonine kinase that is phosphorylated at two sites, Thr 308 (kinase domain) and Ser 473 (C-terminal regulatory region). It is the Ser 473 site that appears to be necessary for maximal activation of Akt(16). We tested the human head and neck cancer cell line SQ20B with a constitutively active EGFR receptor and the human bladder carcinoma cell line T24 with a v12 mutation in H-Ras (Figure 1). At a clinically relevant dose of 5 μ M, NFV down regulated Akt phosphorylation at Ser 473. There was no effect on Akt phosphorylation at Thr 308. Total Akt levels remained constant. Increasing the concentration of NFV slightly increased the onset of the response, but resulted in cell toxicity at 20 μ M. Concentrations in the 5-10 μ M range had no effect on cell growth rate of either T24 or SQ20B cells (data not shown).

[figure not shown]

Figure 1: SQ20B or T24 cells were treated with 5 μ M NFV for 1 or 3 days. Cells were harvested and immunoblotted with antibody used to detect the active or phosphorylated forms of Ser 473 and Thr 308 Akt. Antibody detecting total Akt was also used.

After showing that NFV downregulates P-Akt, we then evaluated radiosensitization in several human tumor cell lines that have EGFR-Ras-PI3K-Akt pathway activation (SQ20B, T24, MIAPACA2, and A549). Rat embryo fibroblasts (REF) were evaluated to assess radiosensitization in cell lines without this pathway activation. Table 1 displays the data from the clonogenic survival curves in tabular form. In every cell line with increased signaling through Akt, there was at least a 19% reduction in surviving fraction with NFV and in many cases the reduction was as large as 40%. There was no change in the radiosensitization of REF cells. Patients treated with radiation generally receive 30 + a treatment of 1.8-2 Gy and the difference is thus exponentially driven. For example, with an SF2 of 0.56 and 30 fractions of 2 Gy, the survival would be 0.56 EE 30 = 2.8 X 10⁻⁸. If the SF2 is 0.45 and 30 fractions of 2 Gy, then the survival would be = 3.95 X 10⁻¹¹. That translates to almost a 3 log difference in the cell kill.

Table 1: Surviving fraction after 2 Gy with and without 5 μ M NFV.

Cell Line	Cancer Type	Mutation	Control SF2 (mean +/- SD)	Nelfinavir SF2 (mean +/- SD)
T24	Bladder	H-Ras	n=6 0.560 +/- 0.061	n=6 0.452 +/- 0.023 p=0.006*
SQ20B	H&N	EGFR	n=6 0.691 +/- 0.042	n=5 0.401 +/- 0.024 p<0.001*
MIAPACA2	Pancreatic	K-Ras	n=4 0.906 +/- 0.086	n=5 0.526 +/- 0.040 p=0.001*
A549	Lung	K-Ras	n=6 0.570 +/- 0.042	n=4 0.401 +/- 0.062 p<0.001*
REF	Rat Fibroblasts	None	n=5 0.408 +/- 0.040	n=5 0.397 +/- 0.054 p=0.89*

* compared to Control SF2 by t-test

Since the effectiveness of cell kill by cis-platinum and etoposide can also be modified with down-regulation of Akt, we tested for sensitization with nelfinavir. T24, SQ20B, and A549 cells were treated with 100, 10, or 1 μ M cis-platinum or etoposide with and without 10 μ M NFV. Sensitization to cis-platinum or etoposide with the addition of NFV was not seen in any of the cell lines. We basically saw one log of cell kill at 1 μ M cis-platinum and 10 μ M of etoposide which was unchanged with the addition of NFV.

In vivo studies were also used to assess radiation sensitization. Mice bearing SQ20B tumors were randomly assigned to each treatment arm (radiation plus drug, radiation alone, drug alone, or mock treatment). Mice were pre-treated for 5 days with oral NFV. The serum concentration of nelfinavir achieved was in the 2-5 μ M range. Figure 2 shows the *in vivo* down regulation of Akt in SQ20B xenografts with NFV. **A** shows immunohistochemistry (400X) of representative SQ20B tumor from a control mouse (left) and a mouse treated with NFV (right). The tumors were harvested 5 days after being treated with placebo or NFV 0.6 mg/day. **B** shows an immunoblot of the lysate from the tumors shown in A.

[figure not shown]
[figure not shown]

Figure 2: *In vivo* down regulation of Akt in SQ20B xenografts. A, immunohistochemistry. B,

For tumor re-growth, 8 Gy was chosen because this dose leads to a growth delay and not a cure thereby permitting the detection for statistical synergy between radiation and drug. The figure on next page shows the data on SQ20B xenografts treated with NFV. The mean tumor volumes are shown in Figure 3A. In the radiation plus NFV group, two slowly growing tumors reached a volume of 1000 mm^3 at 70 and 78 days. The mean time to tumor volume of 1000 mm^3 (Figure 3B) was 11 days in the control group and 12 days in the NFV alone group. As expected, mean values increased in both radiation alone (15 days) and radiation and NFV (41 days) groups. By linear regression analysis, a statistically significant synergistic effect between radiation and NFV was detected (p=0.03).

A**B**

Days to tumor volume of 1000 mm ³ Mean \pm SD (range)			
Control	N	8 Gy	8 Gy + N
$n = 6$	$n = 6$	$n = 5$	$n = 5$
11.0 ± 1.5	12.0 ± 1.5	15.0 ± 2.0	41.0 ± 30.3
(10 – 13)	(10 – 13)	(13 – 17)	(17 – 78)
Test of synergy (one-sided)		$P = 0.03$	

Figure 3: Re-growth delay of SQ20B xenografts +/- NFV after radiation. **A** shows the mean tumor volume in control tumors (○), NFV treated tumors (□), tumors treated with 8 Gy radiation (x), or 8 Gy and NFV treated tumors (◊). **B** is a table that shows mean days to reach tumor volume 1000 mm³ for the 4 treatment groups and the significance of the test of synergy between radiation and NFV.

We evaluated normal tissue toxicity *in vivo* in mice after administration of NFV and radiation. The right leg of each mouse was irradiated with 8 Gy (2 control mice and 2 treated with NFV). We assessed the mice weekly for the visual development of skin fibrosis and leg contractures. No differences were observed in normal tissue toxicity between the 4 groups of extremities (control unirradiated, control irradiated, NFV unirradiated, NFV irradiated). At 60 days, the mice were sacrificed and histological sections of legs were compared. There was an increase in epidermal thickness with irradiation (mean control 16 μ M vs. 22 μ M for 8 Gy). It was however impossible to tell which mouse had been given the NFV vs. control and no additive effect on skin fibrosis was seen with NFV and radiation.

Pre-clinical evidence of immune modulation with NFV and radiation

The tumor regrowth assays with xenografts in nude mice. The combination of nelfinavir and radiation increased time to regrowth compared with radiation alone whereas nelfinavir alone had little effect on tumor regrowth. This radiosensitizing effect was significantly greater than suggested by *in vitro* clonogenic survival assays. One possible explanation for the discordance is that nelfinavir has an immunomodulatory effect in combination with radiation. This is an augmentation of response that would only be evident *in vivo* and not in *in vitro* assays.

Immune modulation with radiation and immune checkpoint (PD-1) inhibition: Preclinical data demonstrate that radiation can improve responses of lung cancer to PD-L1 immunotherapy(4). The mechanisms of cooperation and improved disease control have not been clearly established but may include: (1) enhanced immunogenic antigen presentation (2) stimulation of cytokine release; and (3) enhanced PD-L1 expression on the tumors resulting from change in the stromal lymphocyte infiltration induced by XRT. Blockade of PD-L1 near the time of radiotherapy may enhance the native lymphocyte response. The role of hypofractionated or SBRT-induced tumor antigen release in the era of combination checkpoint inhibition: Higher doses of XRT delivered over shorter fractions have the ability to increase antigen presenting cells (8). Wolchok et al. recently reported a 40% response rate to combination therapy, with all patients achieving greater than 80% or more reduction in tumor burden in advanced melanoma. More recently, blockage of PD-L1 has been demonstrated to be superior to everolimus in advanced renal cell carcinoma with an overall response rate of 25%. This led to the FDA approval of nivolumab as second line therapy in these patients. FDA has rapidly given approval to additional drugs that belong to the same class as nivolumab for its identical clinical indications in melanoma, non-small cell lung cancer, and renal cell carcinoma. In our proposed model, HIGRT/SBRT is complementary to immune checkpoint inhibition and would be anticipated to augment combination therapy.

Immune modulation with dual PI-3 Kinase and Immune Checkpoint (PD-1) Inhibition:

Kim et al investigated epigenetic modulation as a strategy to augment clinical response to immune checkpoint inhibition in a pre-clinical model of CT26 tumors or metastatic 4T1 tumors. Co-treatment with epigenetic-modulating drugs and checkpoint inhibitors markedly improved treatment outcomes, curing more than 80% of the tumor-bearing mice. Functional studies revealed that the primary targets of the

epigenetic modulators were myeloid-derived suppressor cells (MDSCs). Furthermore, they observed that the underlying mechanism driving this improved response was PI3K inhibition and that inhibition of this enzyme reduced circulating MDSCs also eradicated 4T1 tumors in 80% of the mice when combined with immune checkpoint inhibitors.(17) This provides strong pre-clinical supportive data that P-I-3 kinase inhibition can augment response to immune checkpoint blockade.

